## 12.6 Appendix H - Treatment Evaluation: Follow-Up Visit Client's Questionnaire (version 4)

Subject Initials:	Subject ID #:	
Have you delivered vaginally?	Yes / No, if yes, how many_	
Are you sexually active (vaginal intercourse)?	Yes / No, if yes, Av. frequency?	
Question regarding the treatments:	Answers:	
Was the treatment duration tolerable for you?	Yes / No   Too long / Too short	
2. Which of the applicators was most comfortable for you?	External / Internal / Both / None/ None Applicable	
3. How would you describe any sensations you experienced during the treatment? i.e., tingling, warm, hot, burning, itching, etc.	Open answer:	
4. Did you feel intimidated by any of the devices used during the procedure (the treatment equipment / probes/ thermometer etc.)?	Open answer:	
General questions:	Answers:	
5. Did you feel uncomfortable during the procedure (type of treatment, intimacy etc.)? Were you ever alone with your gynecologist?	Yes / No / uncertain / Not applicable Please specify: Yes / No / uncertain	
6. How frequently would you be willing to have Fiore treatments?	Open answer:	
7. What feminine areas for rejuvenation and skin tightening (mons pubis/labia)?	Open answer:	
8. Have you ever experienced similar treatment/s?	Yes / No / uncertain / Not applicable If yes, please specify:	
9. Have you suffered from any of these listed conditions?	Please mark the relevant box/s:  Pelvic prolapse	
10. How long have you experienced any of the above condition/s?	Open answer:	
11.Do you feel that the quality of your sex life is negatively affected by the conditions described above?	Open answer:	
12. Would you consider receiving hormonal therapy to address the above conditions?	Yes / No / uncertain / Not applicable	
13. Have you sought a solution, on your own initiative, to address any of the condition/s described above?	Yes / No / uncertain / Not applicable	
14. Have you spoken with your friends about any of the above condition(s)?	Yes / No / uncertain / Not applicable	
15. Have you considered in the past, or would consider, appropriate surgical solultions for the above medical conditions?	Yes / No / uncertain / Not applicable	
16.In your opinion, what would be the best way to increase awareness for Fiore types of treatments (e.g. TV or radio commercials, Facebook/Internet, magazines ads, news articles, information at physician offices, etc.)	Open answer:	
17. Would you recommend this treatment to your friends?	Yes / No / uncertain / Not applicable	

Confidential 28

## SUBJECT GLOBAL RESPONSE ASSESSMENT SCALE

## Vaginal Tightness

PLEASE CIRCLE THE SCORE THAT BEST DESCRIBES YOUR LEVEL OF VAGINAL	
TIGHTNESS.	
Score	
1	Very loose

Score	
1	Very loose
2	Moderately loose
3	Slightly loose
4	Neither tight nor loose
5	Slightly tight
6	Moderately tight
7	Very tight

PLEASE CIRCLE THE SCORE THAT BEST DESCRIBES HOW YOU NOW FIND YOUR LEVEL OF VAGINAL TIGHTNESS COMPARED TO BEFORE TREATMENTS.	
Score	
1	Markedly Worse
2	Moderately Worse
3	Slightly Worse
4	No Change
5	Slightly Improved
6	Moderately Improved
7	Markedly Improved

## Sexual Satisfaction

PLEASE CIRCLE THE SCORE THAT BEST
DESCRIBES YOUR LEVEL OF SEXUAL
SATISFACTION.

Score	
1	None
2	Poor
3	Fair
4	Good
5	Very good
6	Excellent

PLEASE CIRCLE THE SCORE THAT BEST	
DESCRIBES HOW YOU NOW FIND YOUR LEVEL	
OF SEXUAL SATISFACTION COMPARED TO	
BEFORE TREATMENTS.	

BEFORE TREATMENTS.	
Score	
1	Markedly Worse
2	Moderately Worse
3	Slightly Worse
4	No Change
5	Slightly Improved
6	Moderately Improved
7	Markedly Improved

## Vaginal Dryness

PLEASE CIRCLE THE SCORE THAT BEST
DESCRIBES YOUR LEVEL OF VAGINAL
DRYNESS.

Score	
1	Markedly dry
2	Moderately dry
3	Slightly dry
4	No Change
5	Slightly moist
6	Moderately moist
7	Markedly moist

PLEASE CIRCLE THE SCORE THAT BEST
DESCRIBES HOW YOU NOW FIND YOUR LEVEL OF
VAGINAL DRYNESS COMPARED TO BEFORE
TREATMENTS

Score	
1	Markedly Worse
2	Moderately Worse
3	Slightly Worse
4	No Change
5	Slightly Improved
6	Moderately Improved
7	Markedly Improved

Patient Initials Date (dd/MM/YYYY)

Confidential 29

## 12.7 Appendix I – Additional Safety Background Data

Non-ablative or non-burning RF therapy has been used for vaginal tightening previously within human vaginal mucosa at 75-90 J/m2. (J Sex Med 2010 Sep; 7(9): 3088). For the purpose of this study premenopausal patients will be treated at 90J/m2, whereas the post menopausal patients will be treated with less cumulative heat. We have calculated that the thickness of vagina epithelium (the most susceptible tissue to thermal injury) is decreased 16% in menopause. (This has been calculated by the percent change seen in human vaginal epithelium of menopausal versus non-menopausal on histomorphometry measurements -J. Sex Med 2009 Nov 6(11): 3097.) Reducing energy delivery by 16% yields a safe basement level of 75.6 J/m2 for menopausal patients. Again it is important to emphasize the proposed study device has thermal feedback safety settings and real-time multipolar thermal control to virtually eliminate the possibility of tissue burns. Additionally, now over 3 patients have been treated in Geneva Switzerland with [name], using the proposed study device (Venus Versa) both internally intravaginal and externally. No burns or off target damage was appreciated.

On advisement from the IRB committee and combined with the above information update; for further patient protection we will modify the protocol to perform initial safety parameters on the first 10 patients using 75J/m2 for premenopausal patients and 90J/m2 for premenopausal patients. If these safety parameters are consistent with the preliminary safety studies in Europe, the IRB will review these results, at which time we will submit an expanded study of up to 300 for review.

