## **Study Synopsis**

	· · · ·				
Study Title	Clinical evaluation of the safety and Efficacy of using Multi-Polar RF and PEMF technologies for the treatment of the Mons Pubis, Vaginal Introitus and Labia Skin Laxity				
Protocol No:	CS2815				
Device Name:	Modified Venus Versa (MP)  device with Freeze Diamondpolar and Investigational Applicators				
Design	Feasibility, single-center, baseline-controlled, prospective study				
Projected Study period	Initiation Date: February 2016 Completion Date: February 2017				
Objectives	
 
Primary objectives
 
To evaluate the safety of treating the mons pubis, labia and vaginal introitus with the Freeze Diamond Polar applicator.
 
To evaluate the safety of the internal treatment of the vagina with an investigational applicator
 
To verify the efficacy of using the Freeze Diamond Polar applicator for improving general skin appearance of the mons pubis, vaginal introitus and the labia including improvement of skin irregularities and skin laxity.
 
To determine and/or quantify any potential regenerative properties associated with the study treatments.
 
Secondary objectives
 
To evaluate subject's assessment of comfort and pain associated with treatments.
 
To evaluate subject's satisfaction with treatment results and assessment of improvement.
 
To determine if any regenerative properties are associated with the
 
				
Hypothesis	
 
Mons pubis, Vaginal Introitus and the Labia.
 
The study will confirm that the Freeze Diamondpolar applicator is safe for treating the mons pubis, labia and vaginal introitus which will result in improvement in general skin appearance including an improvement in skin irregularities and skin laxity.
 
The study will confirm that the investigational applicator is safe for
 
				
Study population	internal treatment of the vagina.  1 site with 10 subjects				
Main Inclusion Criteria	
 
Healthy female between the ages of 25 and 65.
 
Sexual activity (vaginal intercourse once per month) in a monogamous relationship.
 
Requesting aesthetic benefit to the vaginal mons, introitus and labia.
 
				

Confidential 2

Protocol: CS2815v4 Approval Number: IRCM-

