### 2 Study Design

This is a single center, baseline-controlled, prospective study. Ten (10) and up to three hundred (300) subjects that meet the inclusion criteria will be enrolled from the site's pool of patients. Subjects should be female, at the age of 25-65 years, and have a suitable treatment area (e.g. skin irregularities and/or unwanted skin laxity in the mons pubis, introitus and/or labia area).

Subjects will receive three treatments with the study device and both applicators, at four week intervals, followed by one month follow-up visits after the last treatment.

Confidential 6

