## 5 Patient Population

### 5.1 Source and Sample Size

Subjects shall be recruited by the investigator from within the investigator's patient population. Subjects shall Confidential

be with skin type I-VI and have unwanted skin laxity in the mons pubis and/or labia area. Each subject (no less than 10 subjects and no more than 300 subjects) included for treatment will receive three treatments at four week intervals and return for follow-up visit at one month (± seven days) after the last treatment for evaluation of the treated areas. Enrolled subjects that did not complete the full course of the study will not be replaced.

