### 8.2 Sample Size Justification

The proposed study is a feasibility study for evaluating the safety and the efficacy of using the Freeze Diamond Polar applicator for treatment of the mons pubis, vaginal introitus and labia anatomical areas and the investigational applicator for treatment of the vagina. Based on previous experience with other RF devices, we believe that the proposed study sample of 10 subjects per each anatomical area (total of 10) will be sufficient to evaluate the safety and the efficacy of the treatment and to obtain qualitative assessments of comfort levels experienced during treatments.

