#### 8.3 Study Analysis

• An intermediate safety report based on qualitative analysis of immediate and short term reaction and on AEs will be produced based on analysis of data collected immediately post treatment number one of all the enrolled subjects. This data will be used to adjust further treatments parameter. The interim

Confidential 14

- reports will not affect the continuation of the study. The study will, regardless of the interim report results, be finalized according to this protocol.
- After FU3, the photographs will be sent to independent evaluators that will grade on a GAI scale the change in skin laxity according to photograph of FU3 compare to baseline. Descriptive statistics and correlations between variables will be performed on these results.
- After FU3 the subject assessment on the change in skin laxity on a GAI scale will be analyzed. These results will be correlated with the evaluation done by the independent evaluators in order to learn on the relationships between objective and subjective improvements assessments.
- After FU3 all data collected by response and discomfort/pain level (VAS) and the 5-level short term response scale results will be analyzed using descriptive statistics.
- After FU3, the vaginal pH values will be sent to the PI for formal data entry and analysis. These results will be correlated with the evaluation done by the independent evaluators in order to learn on the relationships between objective and subjective improvements assessments.
- After FU3, the histology slides and molecular assay results will be sent to the PI for formal data entry
  and analysis and archive storage (histology slides). These results will be correlated with the evaluation
  done by the independent evaluators in order to learn on the relationships between objective and
  subjective improvements assessments.

The study reports will provide information for use in research & development, and future planned studies. Descriptive statistics and correlations between variables will be performed.

Safety: Adverse events reported will be listed, documenting course, outcome, severity, and possible relationship to the treatment.

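### Enrolment is stated as 10, as 10 to 300, and as 10 then up to 300 after IRB review, so subject 11 could be treated before the first-10 safety review

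*Combined protocol and SAP*

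**What the plan says.** Enrolment numbers appear in five places.

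- Study Synopsis: "1 site with 10 subjects".
- Section 8.2: "10 subjects per each anatomical area (total of 10"), justified by previous experience with other RF devices.
- Section 2: "Ten (10) and up to three hundred (300) subjects that meet the inclusion criteria will be enrolled".
- Section 5.1: "no less than 10 subjects and no more than 300 subjects".
- Appendix I: a safety step on the first 10 patients, added on the IRB's advice for further patient protection. It continues: "If these safety parameters are consistent with the preliminary safety studies in Europe, the IRB will review these results". The same sentence then makes a larger study, with a ceiling of 300, the subject of a later submission to the IRB.

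Appendix I describes the European experience with the study device in one place: "now over 3 patients have been treated in Geneva Switzerland", internally and externally, with no burns or off-target damage seen.

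Section 8.3 plans an intermediate safety report on "data collected immediately post treatment number one of all the enrolled subjects". Its stated use is to adjust later treatment parameters. The section adds that interim reports will not affect whether the study continues.

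**The concern.** The first-10 step is the only point at which the protocol foresees a look at the safety of a group of subjects before more women are exposed to the investigational intravaginal applicator. To protect anyone, it has to be found in the sections that govern enrolment. It is not there. Sections 2 and 5.1 give a range running straight through 10 to 300, with no pause, review or approval.

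The wording of the step is a second weakness. The IRB's review is tied to a favourable comparison, what counts as consistent is not defined, and nothing is written for the other outcome. A group review matters most when the results are not reassuring.

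**Working it through.** No sample-size formula applies. The 10 rests on experience and the 300 has no stated basis, so neither can be reproduced. The check is a comparison of texts, with simple arithmetic for size.

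**Step 1. Enrolment statements side by side**

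- Synopsis and section 8.2: maximum 10; expansion not mentioned.
- Sections 2 and 5.1: minimum 10, maximum 300; no stop at 10.
- Appendix I: 10 first, then up to 300 after a further submission.

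The maximum differs by a factor of 300/10 = 30. All of this is operative text, not an amendment log.

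**Step 2. Could another section supply the missing stop?**

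- Section 10.9 requires IRB approval of medically significant amendments. Because sections 2 and 5.1 already contain 300, a site could enrol subject 11 without seeing that an amendment is needed.
- The burn procedure after Appendix I requires a written report to the IRB chairman within 7 days. Section 9.1.6 requires ethics committee notice within 10 working days for anticipated events likely to affect subject safety or study conduct. Both work event by event, and neither pauses enrolment.
- The section 8.3 report covers all enrolled subjects rather than the first 10, and is barred from affecting continuation. If enrolment stays at 10, the two groups coincide.

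**Step 3. Size at the ceiling**

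- Subjects after the tenth: 300 − 10 = 290; 290/300 = 96.7%.
- Sessions at three per subject: 290 × 3 = 870 of 300 × 3 = 900.

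**Step 4. Length of the pause for each possible data cut**

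Appendix A spaces the visits four weeks apart. Counting from the tenth subject's first treatment:

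- Visit 2 cut: 4 weeks.
- FU3 cut: 3 × 4 = 12 weeks.

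IRB time is added to either. Twelve weeks is 12/26 = 46% of the six months in section 7.1, but 12/52 = 23% of the February 2016 to February 2017 period in the synopsis.

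**Context only.** With no events in n subjects, the one-sided 95% upper limit for the true rate is 1 − 0.05^(1/n). That gives 25.9% for n = 10, and 52.7% for n = 4, the smallest number that is more than 3. The European experience is therefore a weak benchmark. The conclusion does not depend on these limits, and no burn rate is assumed.

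**The case against.** The strongest reply is that the document is version 4 and Appendix I is written in the future tense. Sections 2 and 5.1 may be the text after an expansion was submitted and approved, with the synopsis, section 8.2 and Appendix I left behind. The documents neither confirm nor exclude this. It stands as a reason not to demand an unconditional cap at 10. It does not remove the inconsistency, because under that history three other places are out of date.

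A reader might also draw stronger conclusions that the documents do not support:

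- *Poor first-10 results would leave the sponsor free to expand.* Appendix I makes expansion a further submission, so no expansion is the fair inference. The fault is that this is unwritten and that sections 2 and 5.1 contradict it.
- *The IRB would not hear of harm.* Burns and other complications are reportable individually, as are events judged likely to affect safety. Only the group-level review is uncertain.
- *The section 8.3 report is a defective gate.* Nothing in the protocol makes that report the evidence for expansion. Adverse events are recorded at every visit (Appendix A), so later reactions are collected and can be sent to the IRB.
- *The review must wait for FU3.* A Visit 2 cut is defensible. Usual reactions are expected to last hours (section 7.6.1), and the Appendix G questionnaire, which Table 1 schedules before treatment 2, asks about effects out to day 7. FU3 captures all three treatments. This is a trade-off, not an error.

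**Conclusion.** The point holds as an inconsistency with a safety consequence. Read as they stand, sections 2 and 5.1 permit treatment of an eleventh subject before the review that the IRB advised, and the wording of Appendix I makes sending the first-10 results to the IRB depend on their being favourable.

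The figure of up to 290 women, or 870 sessions, is a ceiling. It is reached only if the site enrols to 300 without applying Appendix I, and is not a forecast. The conclusion assumes that approval for expansion is not already in place. If it is, the problem becomes one of outdated text in the synopsis, section 8.2 and Appendix I. Confidence is high on the textual conflict and lower on which number is currently in force. This is a cheap improvement, and it does not undermine the study's analyses.

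**What to change.** 1. **Sections 2 and 5.1.** State that enrolment is 10, and that no subject beyond the tenth is treated until the IRB has reviewed the first-10 safety results and approved expansion to up to 300. If that approval exists, say so and bring the synopsis, section 8.2 and Appendix I into line.
2. **Appendix I.** Remove the condition on consistency. The first-10 safety results, including adverse events recorded after the day of treatment, should go to the IRB whatever they show.
3. **Section 8.3.** Add that the rule that interim reports do not affect continuation does not apply to the expansion decision. The post-treatment-1 report can stay as it is for adjusting parameters.

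The sponsor and IRB should choose the data cut, Visit 2 or FU3, and write it down.

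These are text edits and need no new data collection. The operational cost is a pause in enrolment after subject 10: about 4 weeks with a Visit 2 cut or 12 weeks with an FU3 cut, counted from the tenth subject's first treatment, plus IRB time. Appendix I already implies such a pause, so the edits mainly make it explicit.

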#### SAFETY SOP FOR POTENTIAL BURNS:

The following SOP shall be conformed to at all study facilities if a patient experienced any first, second or third degree burn or pain beyond narcotics:

- 1. The event will be reported to the study Director within 24 hours of occurrence.
- 2. A copy of the patient chart and treatment parameters are to be forwarded to the study Director within 24 hours.
- 3. Immediate triage and treatment of the patient shall be determined by the treating physician and based upon severity and type of burn identified.
- 4. The study Director will be responsible for issuing a written report to the company and the IRB Chairman no later than 7 days from the incident.
- 5. Long term follow up and care shall continue at the discretion of the treating physician.
- 6. All patients experiencing a complication of the device will be followed a minimum of 2 years following the initial injury. Longer care and observation will be at the discretion of the treating physician.
- 7. All minor complications such as appearance or altered sensation, except for pain, can be reported within 30 days of patient complaint. Both chart and treatment parameters are to be provided to the study Director and shared with the company and IRB chairman.

Confidential 30

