#### 7.5 Treatment

All patients will receive treatment of the mons pubis, labia and vaginal introitus with the Freeze Diamondpolar

Confidential 12

Protocol: CS2815v4 Approval Date:

Approval Number: IRCM- Continuing Review Date: February 24, 2017

applicator. Patients will also receive an internal vaginal treatment with the investigational handpiece/applicator.

A dedicated Freeze Diamondpolar applicator will be used for each patient. Each applicator will be clearly labeled with the name of the patient. The patient will take the applicator or disposable head with her at the end of the first treatment session (Tx1) and will bring it back to the clinic for each of the additional treatment sessions (Tx2 and TX3). The applicator should not stay in the clinic possession during the study period. At the end of the study the applicators will return to Venus Concept.

The internal vaginal system consists of an the handheld applicator and disposable cover. The applicator contains 3 pairs of electrodes that deliver the Multi Polar Radiofrequency (RF) and Pulsed Magnetic Fields (PEMF) energy contained in a plastic housing with thermal sensors for detecting the tissue temperature. The disposable cover comes in 2 sizes to accommodate patient sizes.

Based on the mild nature of treatment, anesthesia is not required. Treatment procedure should include positioning of the patient in a manner that enables comfortable access to the treated anatomical site. The positioning of subjects during treatment will be contingent on the location of the treated anatomical site. The following steps should be followed in each treatment session:

- 1. Set the treatment parameters (see Venus Versa (MP) User Manual for the Diamondpolar applicator ). Set the desired energy level between 10%-35% according to the skin type, severity of the treated condition, treatment area, etc. Set conservative parameters for the first treatment, and then gradually increase during treatment or in subsequent treatments according to desired impact, patient's comfort, AEs and results.
- 2. External treatment consists of a multiple passes over the treatment area with treatment parameters adjusted according to patient's comfort and temperature measurements by an external thermometer.
- 3. Move the applicator over the treated area, to maintain a temperature of 40°C-42°C when treating the labia area and 40°C-45°C when treating the monspubis.

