#### 9.1.6 Anticipated Outcome Related Adverse Events

Anticipated adverse events in this study include pain, tenderness, purpura, persistent erythema, edema, burn, blistering, crusting, hyperpigmentation, hypopigmentation, scarring and potential for damage to hair follicles within the treatment area and subsequent loss of hair within the treatment area.

Any anticipated AE that occurs at any time during or after the use of the study device must be recorded by the Investigator. If the anticipated AE, in the opinion of the Investigator, is likely to affect the safety of the subjects or the conduct of the study, the ethic committee will be notified of the effect within 10 working days. In this study if an adverse event occurs the Investigator will continue following the subject until the case is resolved or up to 1 month following the last visit, whichever comes first.

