## 12.5 Appendix E - VAS (Visual Analog Scale)

Check one of the following boxes to indicate tod	day's Treatment Visit:	
Tx1 □ Tx2□ Tx3□		
Immediate Pain Assessment for the Venus Freez	e (MP)  Mons Pubis and Labia procedures:	
Pain assessment of Mons Pubis Please make a mark on the line below to indicato were administered the treatment:	e how much discomfort or pain you experienced when yo	эu
No Pain	Pain as bad as it can be	
Pain assessment of Labia		
Please make a mark on the line below to indicate were administered the treatment:	e how much discomfort or pain you experienced when you	ou
No Pain	Pain as bad as it can be	
Subject Initials/ID Number:		
Date (mm/dd/yy):		
Study Personnel Transcribing V.A.S. Assessment	Scores to Final CRF:	

Confidential 25

Protocol: CS2815v4 Approval Number: IRCM- Approval Date:
Continuing Review Date: February 24, 2017

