## 12.7 Appendix G – Subject Duration of Post Treatment Adverse Events Questionnaire

Check one of the following boxes to indicate today's Treatment/Follow up Visit:  Tx2  Tx3 FU3.							
Please check the box that correlates with the duration of possible post treatment side effects by checking the box that corresponds to the day your symptoms resolved:							
	Day of the Treatment	1 day after	2 day after	3 day after	4 day after	7 day after	
Redness							
Swelling							
Crusting							
Blistering							

Confidential 27

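### Pain below the burn SOP's narcotic threshold has no reporting window inside the SOP, and no subject form shown asks about pain after a session

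*Combined protocol and SAP*

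**What the plan says.** **The SOP (Appendix I, Safety SOP for potential burns).** The opening sentence applies the SOP "if a patient experienced any first, second or third degree burn or pain beyond narcotics". Item 1 sets the fast route: "The event will be reported to the study Director within 24 hours of occurrence". Item 7 sets the slow route: "All minor complications such as appearance or altered sensation, except for pain, can be reported within 30 days of patient complaint". Reports under item 7 carry the chart and treatment parameters to the study Director and are shared with the company and the IRB chairman.

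**Section 9.** Section 9.1 has any adverse event, during or after treatment, entered in the source document and on the CRF. Section 9.1.6 begins its list this way: "Anticipated adverse events in this study include pain, tenderness, purpura, persistent erythema". It makes recording of anticipated events mandatory. It requires notice to the ethics committee within 10 working days when the investigator thinks the event likely to affect subject safety or study conduct. Section 9.1.7 requires immediate telephone notice of serious or unanticipated events, and section 9.2.1 requires serious events to reach the monitor immediately or within 24 hours.

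**The forms.** The Appendix E VAS is completed straight after each session and asks "how much discomfort or pain you experienced when" treatment was being given, with one line for the mons pubis and one for the labia. Appendix G tells the subject: "Please check the box that correlates with the duration of possible post treatment side effects". Its rows are redness, swelling, crusting and blistering. The flow chart schedules adverse event recording at all four visits.

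**The concern.** There are two linked gaps. First, site staff who receive a complaint of pain that is real but short of the narcotic threshold cannot learn from the SOP when to report it. A change in appearance has a stated window and named recipients, while this pain has neither. Second, the one form that asks how long effects lasted leaves out pain and tenderness. Redness, swelling, crusting and blistering can be seen on examination, whereas pain after the subject has gone home can come only from her own account.

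Safety of both applicators is a primary objective (section 3.1). Section 7.5 proceeds on the premise "Based on the mild nature of treatment, anesthesia is not required", and pain that persists after a session bears directly on it. Appendix I sends the results of the first 10 patients to the IRB before an expansion to as many as 300 is submitted. With 10 subjects, one unrecorded case of persisting pain is 1/10 = 10 percentage points of the observed rate.

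**Working it through.** The plan gives no figure to reproduce here. Its analysis is descriptive (section 8.3: "Descriptive statistics and correlations between variables will be performed"), and the point does not depend on sample size, power or error rates. The check sets the passages side by side.

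**Step 1. Which window applies to pain below the narcotic threshold?** The SOP does not define the threshold. Any definition leaves some pain below it, including pain that a narcotic controls.

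| Route | Applies to | Window | Covers non-serious, anticipated pain below the threshold? |
|---|---|---|---|
| SOP opening sentence, item 1 | burns; pain past the threshold | 24 hours | No |
| SOP item 7 | minor complications, pain excepted | 30 days | No |
| Section 9.1 | any adverse event | recording, no deadline | Yes, recording only |
| Section 9.1.6 | anticipated events | recording mandatory; 10 working days if judged likely to affect safety or conduct | Recording yes; deadline only on that judgement |
| Section 9.1.7 | serious or unanticipated events | immediate | No |
| Section 9.2.1 | serious events | immediate or 24 hours | No |

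Such pain must be recorded. It has no reporting deadline unless the investigator makes the section 9.1.6 judgement, and the SOP itself gives it no window.

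**Step 2. Which form asks about pain after a session?**

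| Form | Period asked about | Pain item |
|---|---|---|
| Appendix E (VAS) | while treatment was given | Yes; mons pubis and labia only |
| Appendix F (investigator) | immediately and to about 30 minutes | Tissue response score, no pain item |
| Appendix G (duration) | day of treatment to 7 days after | None |
| Appendix H (questionnaire) | sensations and discomfort during treatment | Not after the session |
| Adverse event CRF page | all four visits | Page not in the documents |

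No subject form shown asks about pain after a session, and the VAS has no line for the introitus or the internal treatment. Yet section 7.6.1 foresees post-treatment discomfort, and sections 9.1.6 and 9.3.1 both name pain and tenderness.

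**Step 3. How many forms?** Appendix G has tick boxes for Tx2, Tx3 and FU3, so three completions per subject. At the minimum enrolment, 10 x 3 = 30 completions; at the maximum, 300 x 3 = 900. Each asks about 4 effects, and 0 of the 4 is pain or tenderness. These are counts of forms, not of missed events, whose number the documents cannot give.

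**The case against.** The strongest reply is that the protocol does catch this pain. Section 9.1 requires every adverse event to be recorded with onset and resolution dates, severity and outcome. Section 9.1.6 makes recording of pain compulsory, and adverse event recording is scheduled at every visit. All of that stands. A reader might infer that lesser pain has no route at all; the documents do not support this, because the gap is in reporting windows, not in the duty to record.

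Three further inferences also go too far.

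- **That nobody asks about pain after a session.** The adverse event CRF page is not in the documents, so its questions are unknown. Only the absence of an item on the subject forms shown is established.
- **That the pain exception in item 7 either frees pain from reporting or forces all of it into 24 hours.** Item 7 grants a permission, and the exception most naturally denies pain that leniency. It then states no alternative window, and the 24-hour figure is not attached to lesser pain anywhere.
- **That the SOP gap by itself makes the safety summary look cleaner.** Section 8.3 lists reported adverse events, not SOP notifications, so a missing SOP deadline removes no recorded pain from that list. The risk to the summary comes from capture, through the forms.

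It may also be said that Appendix G was never meant to be exhaustive, since it omits other anticipated events, such as pigment change and scarring. That is true, but those can be seen at a visit and pain that has resolved cannot.

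**Conclusion.** The point holds in a limited form. Inside the SOP, pain short of the narcotic threshold has no stated reporting window, and section 9 supplies a deadline only conditionally. Separately, post-session pain, including pain after the internal treatment, depends on spontaneous report or on an inquiry whose wording is not shown, while four other effects are asked about by name with their duration.

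The size is modest: one missing row on 30 scheduled questionnaires at 10 subjects, and one unreconciled set of clauses. It is worth correcting because safety is a primary objective and the change costs almost nothing. The conclusion assumes that the forms in the appendices are the complete set of subject forms. If the adverse event CRF page carries a specific question on pain since the last session, the capture part largely falls away and the reporting-window part remains. The condition list in Appendix H, item 9, appears to be cut off in the text available, but that item concerns conditions suffered rather than pain after a session.

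**What to change.** 1. Add a pain/tenderness row to Appendix G, answerable separately for external and internal treatment, on the existing duration columns. State in section 8.3 that it is summarised descriptively with the other rows.
2. Reconcile the SOP's opening sentence, item 7 and section 9 so that every pain complaint has exactly one stated reporting window. Which window applies is for the sponsor, investigator and IRB. Simply striking the pain exception from item 7 is not recommended here: it would put all lesser pain on the 30-day route, and so choose a reporting rule that is theirs to set.

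Cost: one more item on a form already in use, a short edit to the SOP, and probably a few more minor reports.
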